IRB-HSR# 13368: Determining the rapidity with which exogenous P suppresses daytime LH (GnRH) pulse frequency in women during the follicular phase of the menstrual cycle (CRM001)

If three months have elapsed between (a) the subject's most recent safety labs and (b) an overnight admission, a CBC, chemistry and liver panel will be obtained prior to the overnight admission (or on admission) to exclude anemia and any other exclusion criteria.

This study follows a crossover design, with assessment of the acute effects of P and placebo (individually) on GnRH pulse frequency; subjects will be randomized to receive either P or placebo during the first overnight admission, with subsequent overnight study occurring during a subsequent cycle.

Women will begin E2 patches (0.1 mg/d per patch, 2 patches [delivering a total of 0.2 mg/d] placed on the abdomen and changed every 2 d) on the evening of day 4-8 of the study cycle (controls) or  $\geq 4$  days post-menses (PCOS). These patches will be continued for a total of 4 d, with overnight admission occurring on day 3 of E2 administration. Exogenous E2 administration will standardize hypothalamic exposure to E2 and help ensure the presence of sufficient hypothalamic P receptors.

Four to 5 days before a scheduled overnight admission, subjects will come to the CRU or alternate UVA clinical unit for an outpatient blood draw for P and beta-HCG (2 cc). If 30 days will have elapsed between (a) the most recent hemoglobin and hematocrit and (b) the scheduled overnight admission, a hemoglobin and hematocrit will also be drawn at this time (1cc). Note: A hematocrit  $\geq 36\%$  or hemoglobin  $\geq 12$  g/dl in the month before overnight admission is required to participate in the scheduled inpatient (frequent sampling) protocol.

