After 3 d of E2 administration, women will undergo a 24-h sampling study in the CRU, alternate UVA hospital unit, or off-site hotel. Estradiol administration (E2 patches) will continue throughout the overnight admission. Subjects will be admitted to the CRU, alternate UVA hospital unit, or hotel at 1800 h (2 h prior to sampling). Beginning at 2000 h, blood will be obtained through an indwelling i.v. forearm heparin lock over a 24-h period as follows: LH every 10 min (1 ml); P every 30 min (1 ml); FSH, E2, and T every 2 h (assays to be run in same samples as LH and P). SHBG, fasting insulin, and fasting glucose (i.e., fasting since 2200 h) will be run on the 0600 h sample (extra 2 cc drawn). (Subjects will fast from 2200 to 0600 h.) After 10 h of sampling (i.e., at 0600 h), either oral micronized P (100 mg p.o.) suspension or placebo suspension will be administered (according to randomization). (NOTE: the study coordinator will pick up the P/placebo from the research pharmacy to send to the CRU, alternate UVA hospital unit, or hotel the evening before administration.) With exogenous P, we aim to achieve mean plasma P concentrations 4-8 ng/ml. Subjects will not be allowed to sleep during the day (i.e., from 0600 to 2200 h). Subjects will be encouraged to sleep from 2200 to 0600. When possible, sleep will be formally evaluated (extraoculograms, electroencephalograms, wrist actigraphy, etc.)footnote  
. At the completion of sampling, E2 patches will be discontinued. Volunteers will be discharged on oral iron (325 mg BID). We will ask women to eat only the food provided by the CRU staff.

Subjects will undergo another overnight study identical to the first (including pretreatment with E2, outpatient blood draw 4-5 days before admission, etc.), except that oral P will be exchanged for placebo or *vice versa* in accordance with the crossover design. (Subjects will again begin E2 patches on the evening of cycle day 4-8 [controls] or  $\geq 4$  days post-menses [PCOS].) In this way, we will be able to standardize any change in GnRH pulse frequency after P administration to any change in GnRH pulse frequency after placebo administration.

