If the subject does not have hematocrit  $\geq 36\%$  or hemoglobin  $\geq 12$  g/dl shortly before the second scheduled overnight admission, we will offer 1 month of iron treatment (ferrous gluconate 325 mg bid) with a subsequent recheck of hematocrit and/or hemoglobin. If hematocrit and/or hemoglobin are still low, we will offer 1 more month of iron treatment (ferrous gluconate 325 mg bid) with a subsequent recheck of hematocrit and/or hemoglobin. Only volunteers with hematocrit  $\geq 36\%$  or hemoglobin level  $\geq 12$  g/dl (after a maximum of 2 sequential months of iron treatment) will be

---

 Update at time of 5-year renewal April 2017: With regard to the formal sleep evaluation, we have had difficulties obtaining formal polysomnography because of scheduling difficulties with a sleep technician, primarily related to (a) limited availability of sleep technicians for CRU studies and/or (b) increased competition for sleep technicians. For this reason, we have been unable to perform formal sleep studies for the past several years. However, we will routinely perform wrist actigraphy. We will use the Motionlogger Basic-L wrist actigraphy unit (Ambulatory Monitoring, Inc.), which is a watch-like device that contains an accelerometer. This device captures subject movement data, which allows estimation of sleep periods. This watch-like device will be worn on the wrist by the research participant during the CRU admission. There are no known risks associated with wrist actigraphy.

allowed to proceed with the second overnight admission. If three months have elapsed between (a) the subject's most recent safety labs and (b) the second overnight admission, a CBC, chemistry and liver panel will be obtained prior to the overnight admission (or on admission) to exclude anemia and any other exclusion criteria.

The study will end after the second overnight admission. Subjects will be asked to continue oral iron supplementation for at least 30 d after this last overnight admission.

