- Risk of anemia will be reduced in the following manner: A hemoglobin and hematocrit will be obtained and reviewed prior to each CRU sampling study, and only volunteers with a hematocrit  $\geq 36\%$  or a hemoglobin  $\geq 12$  will be allowed to proceed with the frequent sampling study. The one exception to this rule is that those subjects documented to have a hematocrit  $\geq 36\%$  or Hemoglobin  $\geq 12$  g/dl in the month before overnight admission will not be required to have a repeat hematocrit and hemoglobin on overnight admission.
- Risk of fetal exposure to study drugs will be reduced by having a serum pregnancy test obtained and reviewed prior to each overnight sampling study. If the volunteer is pregnant, the study and all study medications will be discontinued.
- A history and physical will be performed at screening. Women with a history of any disorders that may potentially be complicated by long-term iron supplementation, such as hemochromatosis and polycythemia vera, will be excluded. Women with a significant history of cardiac or pulmonary dysfunction (e.g., known or suspected congestive heart failure; known or suspected coronary atherosclerosis; asthma requiring systemic intermittent corticosteroids; etc.) will be excluded. We will exclude women with a history of any disorders that may potentially be complicated by hormonal treatment, such as DVT and breast, ovarian, or endometrial cancer.
- Risk from use of estradiol patch will be reduced by instructing subjects to rotate sites of their E2 patch to avoid skin irritation and/or rash.
- Risk from iron supplementation will be reduced by instructing subjects to take their iron tablets with food and a full glass of water. They will be told to include whole grains and fruits and vegetables in their diet for fiber.
- A comprehensive metabolic panel will be performed at screening. Women with liver enzymes, alkaline phosphatase, or bilirubin  $> 1.5$  times upper limit of normal (confirmed on repeat) will be excluded, with the exception that mild bilirubin elevations will be accepted in the setting of known Gilbert's syndrome. Women with abnormal renal function (i.e., serum creatinine  $> 1.4$ ) will be excluded. Women with abnormal sodium, potassium, or bicarbonate concentrations  $< 20$  or  $> 30$  (confirmed on repeat) will be excluded.

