- If three months have elapsed between (a) the subject's most recent safety labs and (b) an overnight admission, a CBC, chemistry and liver panel will be obtained prior to the overnight admission (or on admission) to exclude anemia and any other exclusion criteria.
- Subjects who are asked to repeat a study admission at a time when they are in the follicular phase of their cycle will be asked to wait the appropriate 8 weeks to schedule the repeat study admission so as not to put the subject at undue risk for anemia. All appropriate safety labs will be obtained prior to studying the subject for a final study admission to ensure subject safety.

- Subjects will have frequent (at least every 10 minutes) contact with CRU nursing personnel and will be asked to report any unusual symptoms occurring during the protocol.

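### The beta-hCG review deadline and the option to draw the 3-month safety panel on admission both fall after the first estradiol patch (minor, cheap to fix)

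*Combined protocol and SAP*

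**What the plan says.** **Pregnancy test.** Section 2.2 of the Data and Safety Monitoring Plan lists, as the measure against fetal exposure to study drugs, "having a serum pregnancy test obtained and reviewed prior to each overnight sampling study". Biomedical Research, question 1, schedules the draw: "Four to 5 days before a scheduled overnight admission, subjects will come to the CRU or alternate UVA clinical unit" for progesterone and beta-hCG. The same draw is repeated before the second admission.

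**Estradiol.** Two 0.1 mg/d patches start on the evening of cycle day 4-8 in controls, or at least 4 days post-menses in PCOS, "with overnight admission occurring on day 3 of E2 administration". The next description of the admission reads "After 3 d of E2 administration, women will undergo a 24-h sampling study". The Drug Information appendix places estradiol under the IND together with progesterone, so it is a study drug.

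**Safety panel.** If three months have passed since the last safety labs, "a CBC, chemistry and liver panel will be obtained prior to the overnight admission (or on admission"). Section 2.2 says this, and Biomedical Research, question 1, says it twice. The paragraph there on the second admission gives the timing and purpose as "prior to the overnight admission (or on admission) to exclude anemia and any other exclusion criteria". Subjects are admitted to the research unit, another hospital unit "or hotel at 1800 h (2 h prior to sampling").

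**Hemoglobin and hematocrit.** These have their own rule. If the last values will be 30 days old by admission, "a hemoglobin and hematocrit will also be drawn at this time", meaning at the 4-5 day visit.

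**The concern.** Each rule states a purpose, and each can be followed to the letter without achieving it.

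The pregnancy test is there to keep a fetus from being exposed to study drugs. Estradiol is the first study drug given, and it starts before the stated review deadline. Nothing in the protocol makes the first patch wait for the result. If a positive result is first read at the deadline, the stated remedy is to stop study medications, which cannot undo the days already worn. The risk table lists the risk to a fetus as unknown and accepts that sexually active subjects may become pregnant during the protocol.

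The three-month panel is there to find women who no longer meet the entry criteria. Drawn on admission, it cannot prevent estradiol exposure in such a woman and leaves little time before blood sampling. Section 2.2 also asks only that the panel be obtained, whereas for the pregnancy test and the hemoglobin it asks for both a result and a review.

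What is at stake is participant safety on a small scale. The trial's inference is not affected.

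**Working it through.** The check is calendar and clock subtraction. Admission is day 0.

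**1. The plan's own interval.** Admission is at 1800 h and sampling starts at 2000 h: 20 − 18 = 2 h. This matches the stated 2 h.

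**2. First patch relative to admission.**
- Cycle days in controls: patch on day 4-8, and admission around day 7-11 (Additional Note in Biomedical Research, question 1). 7 − 4 = 3 and 11 − 8 = 3, so the first patch is at day −3. This agrees with the wording that sampling follows 3 days of estradiol.
- The other wording puts admission on day 3 of estradiol. If the patch evening counts as day 1, 3 − 1 = 2, so the first patch is at day −2.
- Range: day −3 to day −2.

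**3. Beta-hCG draw relative to the first patch.** The draw is at day −5 to day −4.
- Shortest gap: 4 − 3 = 1 day.
- Longest gap: 5 − 2 = 3 days.

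The sample is therefore always taken before estradiol starts. What is missing is a review rule, not an earlier draw.

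**4. First patch to the stated review deadline.** The deadline is the start of sampling on day 0, which is 2-3 days after the first patch. If the result were read only then, nominal estradiol delivery would be 2 × 0.2 = 0.4 mg to 3 × 0.2 = 0.6 mg. This is a worst case under the written rule, not expected practice.

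**5. Panel drawn on admission.**

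| Event | Clock | Relative to an 1800 h draw |
|---|---|---|
| First patch | evening, day −3 or −2 | 2-3 days earlier |
| Panel drawn | 1800 h, day 0 | 0 |
| Sampling starts | 2000 h, day 0 | +2 h |
| Progesterone or placebo | 0600 h, day 1 | +12 h |

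The protocol gives no turnaround time for a panel drawn on admission, so no time to result is calculated here.

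**6. Which values the late panel leaves uncovered.** Hemoglobin and hematocrit are checked within 30 days of sampling and can be drawn at the 4-5 day visit (Biomedical Research, question 1, and the section on drawing more than 500 ml within 48 hours). What remains is mainly chemistry and liver values. Under the exclusion criteria, liver enzymes, alkaline phosphatase, bilirubin, sodium, potassium, bicarbonate and creatinine exclude only when confirmed on repeat. The 2 h before sampling would then have to hold a first result and a second draw.

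**7. Effect of the change.** Requiring both results before the first patch moves each deadline from day 0 to day −3 or −2. The beta-hCG draw needs no new date. A due panel moves from day 0 to the existing visit at day −5 to −4.

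**The case against.** The strongest reply on the pregnancy test is that the schedule already does most of the work. The sample precedes the patch. Pregnancy is an exclusion, beta-hCG is also measured at screening, subjects must be willing to avoid pregnancy, patch start is tied to menses, and all study drugs stop if a subject is pregnant. Section 2.2 is a summary of safeguards, and its outer limit need not be how the unit operates. Harm would require staff to leave unread, for days, a result drawn before the patch.

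This largely stands, and it is why the point is minor. It does not remove the gap. A screening test cannot cover conception before a later admission. The link to menses reassures less in PCOS, where the start window has no upper limit. The written safeguard still allows what it is meant to prevent.

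On the panel, the reply is that drawing on admission is permitted, not required. It arises only when labs are three months old, the woman passed the same tests at screening, and the protocol judges this estradiol course to carry minimal risk. All of that stands. A reader might infer that sampling a woman with one abnormal chemistry or liver value breaks the entry criteria. For most of these values it does not, because a first result excludes no one until it is confirmed. The defect is that the late draw leaves little room for confirmation.

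Three other stronger readings are not supported:
- That pregnant women would routinely receive estradiol. The draw comes 1-3 days before the patch, and prompt reading would normally stop this.
- That anemia goes unchecked before heavy blood sampling. The 30-day hemoglobin and hematocrit rule covers it.
- That repeat admissions escape the pregnancy test. Section 2.2 applies it to each sampling study, and the Additional Note promises all appropriate safety labs before a repeat.

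Nor can one calculate how late a panel result would arrive or how often the panel falls due. The 24 h laboratory figure under Specimen Labeling concerns screening samples. An ordinary cycle length would not describe PCOS subjects, who enter with oligomenorrhea.

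**Conclusion.** The point holds as a minor matter of safety timing. Both latest permitted times, for reviewing the beta-hCG and for drawing a due three-month panel, fall 2-3 days after the first estradiol patch. The panel may be drawn as little as 2 h before sampling.

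For the pregnancy test the expected exposure is none if the result is read promptly. The worst case under the written rule is 2-3 days at 0.2 mg/d. For the panel, the consequence is little time to act on or repeat an abnormal chemistry or liver value, in the subset of admissions where the panel is due and is left until admission. The documents do not give the size of that subset.

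The 2-3 day range rests on the two wordings for when admission falls in the estradiol course. The conclusion is the same under either. No endpoint, power figure or analysis changes.

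**What to change.** 1. In Biomedical Research, question 1, and in section 2.2 of the Data and Safety Monitoring Plan, state that for every admission, repeats included, the first estradiol patch is applied only after the beta-hCG from the 4-5 day draw has been reviewed and is negative.
2. Draw any due three-month CBC, chemistry and liver panel at that same visit and review it before the first patch.
3. Delete the parenthesis that allows the panel on admission, in all three places: twice in Biomedical Research, question 1, and once in section 2.2.

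**Cost.** The 4-5 day visit already exists and already takes hemoglobin and hematocrit when they are due, so a routine panel adds no visit. An abnormal value that needs confirmation does add a repeat draw, and with only 1-3 days before the patch it may delay the start. A late beta-hCG result would do the same. In controls the start window is five evenings (cycle days 4 to 8), so a delay past day 8 moves that admission to a later cycle. The April 2017 update says controls are complete, however, and the PCOS window has no upper day limit. The remaining cost is therefore an occasional delayed patch start and repeat draw in the last PCOS participants.

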**To minimize the risk of having >500 ml of blood drawn within 48 hours:**

A hemoglobin level will be drawn within 30 days prior to the visit at which the blood will be drawn. The blood will not be drawn if the levels do not meet the criteria below:

- Hematocrit at least 36% and/or a hemoglobin level at least 12 g/dl

**2.3 Under what criteria would an INDIVIDUAL SUBJECT'S study treatment or study participation be stopped or modified**

At subject, PI or sponsor's request (see below)

- If the volunteer is pregnant, the study and all study medications will be discontinued.
- Estradiol will be discontinued and the study stopped if side effects (e.g., nausea, breast tenderness) become problematic.
- If subjects remain anemic (HCT < 36% and hemoglobin < 12) after 2 sequential months of ferrous gluconate (325 mg bid), they will then be excluded from participation in the study.

Treatment would be stopped if the subject had a serious adverse event deemed related to study, or study drug will be increased if the subject tolerates dosing

Refer to the non- IRB Protocol (Sponsor's, Investigator-Initiated, CTEP protocol etc.)

**2.4 Under what criteria would THE ENTIRE STUDY need to be stopped?**

**INSTRUCTIONS;**

- These are called stopping rules for early termination of the entire study.
- List criteria regardless of whether the study is sponsored or not.
- Be sure to include any criteria for which the UVa PI would halt the study at UVa.
- Check all that apply.

Per IRB, PI, DSMB, or sponsor discretion

Two (2) subjects having serious, unexpected related or possibly related Adverse events.

**2.5 What are the criteria for breaking the blind/mask?**

Other: If a severe adverse event occurs within 24 hours after administration of progesterone/placebo.

**2.6 How will subject withdrawals/dropouts be reported to the IRB prior to study completion?**

IRB-HSR continuation status form

**3. Adverse Event / Unanticipated Problem Recording and Reporting**

**3.1 Will all adverse events, as defined in section 1.1, be collected/recorded?**

► **IF NO, what criteria will be used? No**

Only adverse events deemed related/possibly related to study

Only adverse events that are deemed serious

Only adverse events that are deemed related AND serious

**3.2 How will adverse event data be collected/recorded?**  Check all that apply

Paper AE forms/source documents

Spreadsheet: paper or electronic

Database  **Answer/Response:**

**3.3. How will AEs be classified/graded?**  Check all that apply

World Health Organization Criteria (WHO)

NCI Common Toxicity Criteria, Version 2.0/ NCI Common Terminology Criteria, Version 3.0

NCI CTCAE Version 4.0

Mild/Moderate/Severe

Serious/Not serious

**3.4 What scale will the PI use when evaluating the relatedness of adverse events to the study participation?**  Check all that apply.

The PI will determine the relationship of adverse events to the study using the following scale:

Related:	AE is clearly related to the intervention
Possibly related:	AE may be related to the intervention
Unrelated:	AE is clearly not related to intervention

**3.5 When will recording/reporting of adverse events/unanticipated problems begin?**

After subject begins study drug/ device placement/intervention /study-related procedure/specimen collection

**3.6 When will the recording/reporting of adverse events/unanticipated problems end?**

End of study drug/device/intervention/participation

30 days post study drug/device/intervention

Subject completes intervention and follow up period of protocol

**3.7 How will Adverse Events, Unanticipated Problems, Protocol Violations and Data Breaches be reported? Complete the table below to answer this question**

IRB-HSR# 13368: Determining the rapidity with which exogenous P suppresses daytime LH (GnRH) pulse frequency in women during the follicular phase of the menstrual cycle (CRM001)

Type of Event	To whom will it be reported:	Time Frame for Reporting	How reported?

Any internal event resulting in death that is deemed DEFINITELY related to (caused by) study participation  An internal event is one that occurs in a subject enrolled in a UVa protocol
	IRB-HSR	Within 24 hours	IRB Online and phone call  www.irb.virginia.edu/

Internal, Serious, related/possibly related, Unexpected adverse event
	IRB-HSR	
Within 7 calendar days from the time the study team received knowledge of the event.
 
Timeline includes submission of signed hardcopy of AE form.
	IRB Online  www.irb.virginia.edu/

Unanticipated Problems that are not adverse events or protocol violations  This would include a Data Breach.
	IRB-HSR	Within 7 calendar days from the time the study team received knowledge of the event.	
Unanticipated Problem report form.
 
http://www.virginia.edu/vprgs/irb/HSR_docs/Forms/Reporting_Requirements-Unanticipated_Problems.doc )


Protocol Violations/Noncompliance  The IRB-HSR only requires that MAJOR violation be reported, unless otherwise required by your sponsor, if applicable.
 
OR
 
Enrollment Exceptions  See definition- only allowed if there is a commercial sponsor or a DSMB that has granted the enrollment exception.
	IRB-HSR	Within 7 calendar days from the time the study team received knowledge of the event.	
Protocol Violation, Noncompliance and Enrollment Exception Reporting Form
 
http://www.virginia.edu/vprgs/irb/hsr_forms.html
 
Go to 3rd bullet from the bottom.

Data Breach
	
The UVa Corporate Compliance and Privacy Office
 
ITC: if breach involves electronic data
	
As soon as possible and no later than 24 hours from the time the incident is identified.
 
As soon as possible and no later than 24 hours from the
	
UVa Corporate Compliance and Privacy Office- [contact]
 
ITC: Information Security Incident Reporting procedure, http://www.itc.virginia.edu/security/reporting.html

	
Police if breach includes items that are stolen:
 
Stolen on UVA Grounds
 
OR
 
Stolen off UVA Grounds- contact police department of jurisdiction of last known location of PHI
	
time the incident is identified.
 
IMMEDIATELY.
	
UVa Police-Phone- [contact]

--	---	---	---

**4. How will the endpoint data be collected/recorded.** Check all that apply

- Protocol specific case report forms
- Source documents

